### **Infant carriage**

With the exception of *Klebsiella*, which is tested for in NPS and RS, in samples collected from infants each bacteria is only tested for in one sample type (e.g. *S. pneumoniae* is tested for in NPS and *E.coli* is tested for in rectal swabs). Therefore, in contrast to the analysis of maternal carriage, there is no need to combine results across different sample types. Each bacteria will be compared between study arms at day 0, day 6, day 28 and 4 months (Table 4). Additionally, we will compare the proportion positive at any time point. We will use logistic regression to adjust for maternal carriage at day 0 if the prevalence is  $\geq 4\%$ , if the prevalence is less than this then we will calculate an unadjusted OR and use Fisher's exact test. Note that we have chosen to adjust for maternal carriage at day 0 rather than neonatal carriage because neonatal samples are collected after treatment and may, therefore, be affected by treatment. The prevalence at each time point and in each arm will be displayed graphically. As with the analysis of maternal carriage, the analyses will be

done in children with complete data and then repeated using multiply imputed data (missing day 28 and 4-month outcomes will be imputed from day 0 and day 6 outcomes).

### Carriage of resistant isolates

The analysis of resistant strains in the mother and neonate will mirror the analysis of overall carriage. Resistance will be defined using the E-test resistance cut-offs defined in Table 7 below. The prevalence of resistance can be defined either in terms as the proportion of resistant isolates among carriers or as the proportion among all individual (carriers + non-carriers). In this analysis, we will use the number of individuals tested as the denominator.

**Table 7** E-test cut-offs used to define resistance to azithromycin

Bacteria	Cut-off ( $\mu\text{g}/\text{mL}$ )		
	Sensitive	Intermediate	Resistant
E. coli	$\leq 16$	16	$\geq 32$
Klebsiella spp	$\leq 16$	16	$\geq 32$
Pseudomonas	$\leq 16$	16	$\geq 32$
S. aureus	$\leq 2$	4	$\geq 8$
S. pneumoniae	$\leq 0.5$	0.5	$\geq 1$
GBS	$\leq 0.5$	0.5	$\geq 1$
GAS	$\leq 0.5$	0.5	$\geq 1$

### 8.3 Anthropometric cohort

Standardised anthropometric Z-scores (WHZ, WAZ, HAZ and MUAC-for-age, head-circumference-for-age) based on WHO 2006 growth charts will be calculated using the Stata package “zanthro” (Vidmar et al., 2013).

As recommended in the WHO report on data quality in anthropometric studies

<https://www.who.int/nutrition/publications/anthropometry-data-quality-report-chapter3.pdf>, a flag system will be used to recode implausible z-score values as missing:

- height-for-age:  $< -6$  or  $> +6$
- weight-for-length/height:  $< -5$  or  $> +5$
- weight-for-age:  $< -6$  or  $> +5$

- body mass index-for-age:  $< -5$  or  $> +5$

For each anthropometric measure, we will compare between study arms the mean score at 6 months, 12 months, and growth velocity, i.e. difference between 6 and 12-month scores. Linear regression will be used to calculate a difference between arms and p-value adjusted for country, birth weight and 1-minute Apgar score. The continuous variables (birth weight and Apgar score) will be included in the model as linear terms.

In addition, we will dichotomise the Z-scores using  $< -2$  SD as the cut-off for malnutrition and  $< -3$  SD as the cut-off for severe malnutrition. We will use logistic regression to adjust for country, birth weight and 1-minute Apgar score.

## 9 Safety Analyses

We will report the numbers of severe adverse, hospitalisations and deaths in mothers and neonates in the Primary cohort and number of deaths in the Carriage and Anthropometric cohorts. When calculating the incidence, each subject will be counted only once and any repetitions will be ignored; the denominator will be the total population size. P-values will be calculated using Fisher's exact test.

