#### Safety objectives

To evaluate the safety of the intervention through active and passive surveillance for adverse events (AE) in mothers and newborns during the 28-day follow-up period. All newborns with history of projectile vomiting will be thoroughly assessed for hypertrophic pyloric stenosis (HPS).

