### Safety endpoints

1. Solicited and unsolicited AEs observed or reported in mothers in the 28 days after treatment.
2. Solicited and unsolicited AEs in newborns observed or reported in the first 28 days after birth.
3. AEs reported among infants followed up to 1 year.

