### 4.4 Study Variables

(ICH E3; 9.5.1. ICH E9; 2.2.2)

The study activities for all mother–newborn dyads/triads enrolled in the study are summarised in the table below (Table 1). In the subset enrolled in the carriage sub–study (n=250 per country), additional home visits were conducted at day 6 and 4 months, and in the subset enrolled in the anthropometrical sub–study (n=1,000 per country) additional home visits were conducted at 6 and 12 months. Surveillance for deaths, sepsis and adverse events was up to day 28 for all participants. In addition, for participants in the carriage sub–study, surveillance for deaths and serious adverse events extended to 4 months, and for participants in the anthropometric sub–study surveillance extended to 12 months.

Note that day 0 is the date of birth rather than date of randomisation as in the study protocol. We have chosen to re–define follow up time as time from birth rather than time from randomisation to ensure that the definition of neonatal sepsis—one of the components of the primary outcome—is consistent with the standard definition.

**Table 1** Summary of study activities

	Pregnancy	Day 0  or Day -1 or Day 1	Day 28 (±4days)
Sensitisation & consent	X		
Health facility visit for delivery		X	
Review of inclusion & exclusion criteria		X	
Randomisation & treatment		X	
Discharge review		X	
Active follow–up (home visit)			X
Passive surveillance 		—————→	

Day 0 is defined to be the day of birth. Note that randomisation and discharge might not occur on the same day as the delivery.

Passive surveillance for adverse events, mortality and sepsis. The surveillance period extends to 4 months for mothers and children participating in the carriage sub–study and to 12 months for children participating in the anthropometrical sub–study.

**Table 2** Carriage samples collected from mother–newborn pairs (n=500; 250/country) enrolled in the carriage sub–study

	Day 0  (or Day –1)	Day 6 (±2 days)	Day 28 (±4 days)	4 Months (±2 weeks)
Mother				
Recto–Vaginal	X 			
Nasopharyngeal	X 	X		
Oropharyngeal	X 	X		
Breast milk		X	X	X
Newborn				
Nasopharyngeal	X 	X	X	X
Oropharyngeal	X 	X	X	X
Rectal	X 	X	X	X

Samples collected on the day of birth (baby) or randomisation (mother) were collected at the health facility. Note that randomisation often occurred the day before delivery.  

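### Section 9 does not analyse the safety endpoints as Section 3.4 defines them, plans no summary of pyloric stenosis, and counts sub-study deaths in cohorts restricted to survivors

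*SAP*

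**What the plan says.** SAP Section 3.4 (Safety endpoints) lists three items:

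- "Solicited and unsolicited AEs observed or reported in mothers in the 28 days after treatment"
- "Solicited and unsolicited AEs in newborns observed or reported in the first 28 days after birth"
- "AEs reported among infants followed up to 1 year"

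The safety objective in Section 3.3 covers AE surveillance in mothers and newborns over 28 days and singles out one event: "All newborns with history of projectile vomiting will be thoroughly assessed for hypertrophic pyloric stenosis (HPS").

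Section 4.4 describes what was watched for. Surveillance to day 28 in all participants covered deaths, sepsis and AEs. For the carriage sub-study, "surveillance for deaths and serious adverse events extended to 4 months", and for the anthropometric sub-study surveillance ran to 12 months.

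Section 9 is a single paragraph. For the main cohort it says "We will report the numbers of severe adverse, hospitalisations and deaths in mothers and neonates in the Primary cohort". For the sub-studies it plans only the "number of deaths in the Carriage and Anthropometric cohorts". Each subject is counted once, the denominator is the whole population, and "P-values will be calculated using Fisher's exact test".

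**The concern.** The endpoint list and the analysis section of one document should match, and here they do not. Section 3.4 promises AEs as a class, split into solicited and unsolicited and followed to 1 year in a subset of infants. Section 9 plans a narrower set, and its one AE category lacks a noun and a definition. The event that the safety objective names is not in the analysis at all.

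Three things are at stake:

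- The choice of which AE tables to produce is left open, so it could be made after the code is broken.
- An analyst cannot tell from the text whether to select events by severity grade or by seriousness. These are different classifications and can give different counts.
- Non-fatal events found in the extended sub-study follow-up have no planned comparison between arms. Part of the planned comparison of deaths there cannot yield any information.

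**Working it through.** The point needs no power, rate or significance level, and the SAP gives no figure to reproduce. The check sets the sections side by side.

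**Step 1: each endpoint against Section 9.**

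- *Maternal solicited and unsolicited AEs, 28 days after treatment.* Section 9 gives the *severe adverse* category, hospitalisations and deaths. There is no summary of all solicited or all unsolicited AEs, so only a subset is covered.
- *Newborn solicited and unsolicited AEs, first 28 days.* The same holds.
- *Infant AEs to 1 year.* Section 9 gives deaths in the Anthropometric cohort. No non-fatal event is covered.
- *HPS.* It appears in the Section 2 abbreviations and the Section 3.3 safety objective. It is in neither the Section 3.4 list nor Section 9, so no summary is planned.

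Three of three listed endpoints are therefore not analysed as defined, though none is wholly ignored.

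**Step 2: what Section 9 adds to the efficacy analysis.** Neonatal hospitalisation, maternal hospitalisation and maternal mortality are already secondary endpoints in Section 3.4, and so is 12-month all-cause mortality in the anthropometric cohort. The main new safety content is all-cause neonatal deaths and the *severe adverse* category.

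**Step 3: the term.** The SAP defines no severity grade for AEs. Section 4.4 speaks of AEs to day 28 for everyone and uses *serious* only for the extended sub-study follow-up. Footnote 2 of Table 1 describes that same extended surveillance as covering AEs, without *serious*. The scope of collection after day 28 is thus worded in two ways, and Section 9 uses a third word.

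**Step 4: who can contribute a death.** Section 6.2 sets the cohorts:

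- *Carriage cohort:* every member of the dyad or triad must be alive and still participating at the 4-month visit. Any family with a death before that visit is outside the cohort, so deaths counted up to that visit = 0 in both arms, whatever happened.
- *Anthropometric cohort:* the infant must be alive and participating at day 28, so only later deaths can be counted.
- *Primary cohort:* deaths to day 28 are included. Early deaths among sub-study infants can therefore appear there. Deaths between day 28 and the 4-month visit in carriage-only families appear in no Section 9 count.

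**Step 5: numbers concerned.** Sections 3.4 and 4.4 give 250 pairs per country for the carriage sub-study: 2 × 250 = 500 dyads or triads. For the anthropometric sub-study, Section 4.1 gives the first 2,000 women and Section 4.4 gives 1,000 per country (2 × 1,000 = 2,000), but the Section 3.4 heading gives 1,000 infants. The extended infant follow-up therefore concerns 1,000 to about 2,000 infants, depending on which statement is right. The 28-day endpoints concern all 12,000 women and their newborns.

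**The case against.** The best defence is that Section 9 holds the most important events. It gives a severe category, hospitalisations and deaths for mothers and neonates, with a counting rule, a denominator and a test. This stands in part, and it rules out a reading some will be tempted by: that the trial could not answer its own safety objective. That objective is to evaluate safety through surveillance, and Section 9 does provide a partial evaluation.

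A reader might also infer that *severe* contradicts *serious*. The text does not show it. Section 9 applies *severe* to the Primary cohort, whose 28-day surveillance was for AEs without restriction. Section 4.4 applies *serious* only to extended sub-study follow-up, where Section 9 speaks of deaths. The two words never describe the same cohort and period. A slip for *serious* is plausible but unproven, and the missing noun may have been lost when the PDF was read. What remains is that the term is undefined.

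Nor should HPS be called an endpoint that was dropped. It is not in the Section 3.4 list; Section 3.3 presents it as an assessment within the safety objective.

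Two further defences carry less weight. Section 7 refers to dummy tables that are not shown and may contain AE layouts, but Section 9 does not cite them. This lowers certainty without closing the gap. Solicited and unsolicited AE forms also feed the skin, eye, umbilical, ear and mastitis definitions in Section 4.4, but those serve infection endpoints and do not replace an overall AE summary.

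**Conclusion.** The point holds as a mismatch inside the SAP between its safety endpoints and its safety analysis. None of the three listed endpoints is analysed as defined, HPS has no planned summary, and the only AE category is incomplete and undefined. In addition, the Carriage-cohort death count is zero by construction up to the 4-month visit, and the Anthropometric count leaves out deaths before day 28.

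This is a gap in safety reporting that should be closed. It does not touch the primary efficacy analysis. The conclusion assumes that Section 9 is the operative safety plan, that the unseen dummy tables do not override it, and that Section 9 uses the cohorts as Section 6.2 defines them.

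**What to change.** Rewrite Section 9, before the code is broken, to report by arm with each subject counted once:

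- any solicited AE and any unsolicited AE, separately for mothers and for newborns, to day 28;
- the number of HPS cases;
- AEs to 12 months in infants selected for the anthropometric sub-study, saying whether all AEs or only serious ones were collected after day 28;
- serious AEs and deaths to 4 months among everyone selected for the carriage sub-study, not the survivor-restricted Carriage cohort.

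Replace *severe adverse* with a complete term (serious, severe or both), define it, and make it agree with Section 4.4 and footnote 2 of Table 1. If the dummy tables already contain these summaries, cite them in Section 9. A by-arm summary is enough to close the gap; Fisher p-values for every AE class are optional.

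The cost is a few more tables from events that the SAP says were under surveillance. The number of HPS cases depends on how the assessments were recorded, which the SAP does not state.

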#### Anthropometric cohort (1,000 infants) – follow-up for 12 months

1. All-cause mortality
2. Malnutrition (day 28, 6 and 12 months) – Height-for-age z-score (HAZ), weight-for-age z-score (WAZ), weight-for-height z-score (WHZ), body mass index-for-age, head circumference-for-age, and mid-upper arm circumference for age (MUAC)

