### **Anthropometric cohort**

The cohort will include all infants who meet the following criteria:

- Selected to be in the anthropometric cohort
- Included in the primary analysis cohort
- Alive and participating in the study at day 28

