### Carriage and Anthropometric cohorts

Since outcomes are actively recorded in these cohorts, missing data may be recorded for some of the outcomes analysed in the Carriage and Anthropometric cohorts.

We anticipate some missing data at the 4-month time point because of the interruption due to the COVID-19 pandemic. Therefore, an available case analysis will be conducted in the Carriage cohort. The occurrence of missing data is unlikely to be associated with any particular characteristic of the women/neonates, and the risk of bias due to missing data is small.

The anthropometric cohort was recruited prior to the COVID-19 pandemic. Nevertheless, we expect some missing data due to loss to follow up, and will therefore conduct an available case analysis in this cohort. We will assess the risk of selection bias by comparing the baseline characteristics of children who are lost to follow up with those who remain in the cohort throughout follow up.

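### Section 9 divides Anthropometric-cohort deaths by the total population, so infants lost after day 28 whose deaths go uncaptured count as 12-month survivors (minor)

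*SAP*

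**What the plan says.** - **Endpoint.** Section 3.4 lists "All-cause mortality" first under "Anthropometric cohort (1,000 infants) – follow-up for 12 months". Section 4.4 confirms the period for deaths: "for participants in the anthropometric sub–study surveillance extended to 12 months". Section 4.1 gives all-cause mortality as one purpose of the 6- and 12-month visits.
- **Cohort.** Besides selection for the sub-study and membership of the Primary cohort, section 6.2 requires only "Alive and participating in the study at day 28". It sets no condition on later follow-up.
- **Expected losses.** For this cohort, section 6.4 says "we expect some missing data due to loss to follow up" and announces an available-case analysis.
- **Analysis of deaths.** Section 9 promises the "number of deaths in the Carriage and Anthropometric cohorts", counts each subject once, and says "the denominator will be the total population size". It adds: "P-values will be calculated using Fisher's exact test".
- **Efficacy section.** Section 8.3 covers z-scores, their change between 6 and 12 months, and their dichotomised forms. It does not mention mortality.
- **General rule.** Section 6.3 assigns logistic regression to binary outcomes and lists country, Apgar score and birthweight as covariates for the Primary and Anthropometric cohorts. Section 6.6 repeats the adjustment.

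**The concern.** A fixed denominator is sound when every member's status is known at the end of the period. The SAP relies on this for day-28 mortality: section 8.1 explains that no censoring is needed because neonates of unknown day-28 status are excluded from the Primary cohort. No such condition holds between day 28 and 12 months. An infant who withdraws or moves away at month 3 stays in the denominator and contributes no death, whatever happens later.

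Two things are at stake. The reported 12-month mortality would be too low. And the SAP would hold more than one possible denominator and method for a listed endpoint, leaving the choice to be made at analysis.

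**Working it through.** **Which text governs 12-month mortality.** Section 9 is the only place that names deaths in this cohort. Fisher's test needs a count of non-deaths as well as deaths, and the only denominator section 9 supplies is the total population. Sections 6.3, 6.4 and 6.6 can be read as giving an adjusted, available-case logistic regression instead. The two routes treat an infant of unknown 12-month status differently: the first scores the infant as a non-event, the second drops the infant. The SAP does not say which applies.

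**Figures available.** The SAP states no 12-month mortality and no loss rate after day 28, so there is no figure of its own to reproduce. Its only loss figure is the 8% allowed in the original sample size (section 5), which is not specific to this cohort or period. The inputs below are assumptions:

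- m, the true risk of death from day 28 to 12 months: 2.0%.
- L, the loss by 12 months: 8% to 30%.
- No death after loss is captured.

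**Constant hazards.** Let h = -ln(1 - m) = -ln(0.98) = 0.0202 and l = -ln(1 - L). The proportion obtained with the full denominator is h/(h + l) × (1 - exp(-(h + l))).

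| L | l | h + l | 1 - exp(-(h + l)) | Reported risk | Share of true 2.0% |
|---|---|---|---|---|---|
| 8% | 0.0834 | 0.1036 | 0.0984 | 1.92% | 0.960 |
| 10% | 0.1054 | 0.1256 | 0.1180 | 1.90% | 0.949 |
| 20% | 0.2231 | 0.2433 | 0.2160 | 1.79% | 0.897 |
| 30% | 0.3567 | 0.3769 | 0.3140 | 1.68% | 0.842 |

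The relative shortfall is about L/2.

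**Upper bound.** If all losses fell just after day 28, the reported risk would be m(1 - L): 1.84% at 8% loss, 1.80% at 10% and 1.60% at 20%. The relative understatement therefore lies between about L/2 and L.

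**Comparison of arms.** With equal loss in both arms the shortfall cancels, and with no true effect the risk ratio stays at 1.00. With no true effect, 10% loss in one arm and 20% in the other, the risk ratio is 1.90/1.79 = 1.06.

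**Set against sampling error.** Sections 4.1 and 4.4 put the sub-study at 2,000 (1,000 per country), so about 1,000 per arm. The reported risks then give about 19 and 18 deaths. The standard error of the log ratio is √(1/19 + 1/18 - 2/1000) = 0.326, and the 95% interval for the ratio 19/18 = 1.06 is about 0.56 to 2.0. If the total is 1,000, as the section 3.4 heading says, the interval is wider still.

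**The case against.** The strongest counter-argument is that section 9 is only a safety tabulation. For this cohort it promises a number of deaths, its denominator sentence is a generic convention about counting each subject once, and it does not define the total population. The endpoint analysis, on this view, is the adjusted logistic regression of sections 6.3 and 6.6 on available cases under section 6.4, so infants of unknown status drop out. That reading is open, and a flat claim that 12-month mortality can only fall under section 9 would go too far. But it leaves two rules for one listed endpoint, and section 8.3 does not settle which applies.

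Second, surveillance for deaths runs to 12 months independently of the visits, so a missed visit is not necessarily a missed death. This stands. The figures above apply only to deaths that surveillance fails to capture.

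Third, a reader might infer that the treatment comparison is biased. The SAP does not support that. Such bias needs loss that differs by arm, and nothing in this double-blind, single-dose trial's plan suggests it.

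Fourth, Kaplan-Meier does not cure informative loss. Also, censoring survivors at their last visit while deaths are reported at any time can overstate risk. Both points are fair. The second is met by taking the last known vital status from visits and surveillance together.

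**Conclusion.** The point holds as a minor one. As written, section 9 scores as survivors those infants lost after day 28 whose deaths go uncaptured, and the SAP's own reason for needing no censoring stops at day 28. The absolute 12-month risk is understated by about half the loss fraction in relative terms if loss is spread over follow-up: about 5% at 10% loss and 10% at 20%. At an assumed true risk of 2.0%, that is about 0.1 and 0.2 percentage points. These sizes rest on assumed mortality and loss rates, constant hazards and no capture of deaths after loss. Distortion of the risk ratio is conditional on unequal loss and would be small beside sampling error. The conflict with sections 6.3, 6.4 and 6.6 is conditional too: it exists if those sections are meant to cover mortality, which the SAP should state.

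**What to change.** In section 9, limit the total-population denominator for deaths to day-28 deaths in the Primary cohort.

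In sections 8.3 and 9, state for the Anthropometric cohort that:

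- 12-month mortality is reported by arm as a Kaplan-Meier risk, starting at day 28 because entry requires being alive then;
- infants are censored at the last date on which vital status is known from visits or surveillance, by the same rule in both arms;
- the number lost is given per arm;
- a sensitivity analysis uses only infants with known 12-month status;
- this analysis, and not the general rule in sections 6.3, 6.4 and 6.6, governs the mortality endpoint.

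The cost is a few sentences and one table from visit, surveillance and death dates. The interval becomes slightly wider, and the analysis still assumes that loss is non-informative. The primary outcome is untouched.
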